Postural instability is preferably investigated using objective measures of posturography, the advantages of which over regular clinical assessments include the reduction of test performance variability and avoidance of subjective scoring systems.¹² Recently, researchers have analyzed the performance of the Wii Balance Board (WBB; Nintendo, Kyoto, Japan) in the measurement of postural instability; WBB-based assessment has shown excellent concurrent validity and the ability to complement existing fall assessments.^{13,14}

As of 2012, all 70-year olds in the Umeå municipality are invited to participate in the Healthy Ageing Initiative (HAI) study, which has currently enrolled more than 3000 participants.

Among other measurements, we include assessment of postural stability using a Wii Balance Board (WBB; Nintendo, Kyoto, Japan) device. With each participant in a quiet stance, balance trials consisting of 60-second eyes-open (EO) and eyes-closed (EC) trials are performed. Participants are instructed to maintain an upright position throughout the test, stand relaxed, and avoid any arm or head movement. The WBB measures total COP sway length, representing the sum of postural sway in the anteroposterior and mediolateral directions.

Preliminary results from our analysis of data consisting of 1900 70-year-old individuals revealed that participants with postural sway in the 5th quintile had almost twice the risk of

falling compared to the reference group, when the 1-year follow-up of prospective falls was performed.

Thus the aim of the present follow-up study is to investigate if we can reduce the increased postural sway of participants who have been identified as having abnormal balance values, based on previous measurements.

Project description

Study design

The present project is planned to be conducted as a 4-week randomized intervention study with a follow up time of 2 years.

Study population

Recruitment of individuals at high risk of falls from the Healthy Ageing Initiative

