The Healthy Ageing Initiative (HAI) is an ongoing population based project aiming to reduce risk factors for non-communicable diseases (NCD) by risk factor evaluation and increased physical activity.¹⁵ In short, HAI is inviting all 70 year olds in Umeå municipality to a health examination where traditional and potential novel risk factors for diabetes, CVD and fractures are investigated. These include objective measures of physical activity, blood pressure, blood-glucose, objective measured abdominal fat mass and ectopic fat, bone density and other features of bone quality, cognitive function, balance, walking ability, and different life style factors. At the second visit, all participants are informed about the results of tests performed and gets advice with a focus on physical activity, aiming at decreasing the risk of future diabetes, CVD and fractures. The counseling with focus on physical activity is based on motivational interviewing (MI) which is a directive patient-centered counseling style to help the participants to explore and resolve their ambivalence about behavior change. They are

contacted at 6 months and 12 months per telephone for follow up and are contacted for an in-clinic follow up after 5 years.

Participants in HAI identified as being in the highest quartile of measures of postural sway, indicating poor balance and high fall risk, are invited to participate by telephone contact, and will upon agreement be randomized into either the intervention group or control group.

Participants will after the initial contact also receive written information about the study. We aim to recruit 90 individuals from the existing HAI study cohort

Study protocol

Please see figure 1 for figure of study protocol.

Intervention protocol

Group 1

Twenty participants are randomised into the intervention group. The intervention group will perform group training sessions a week, consisting of 30 minutes of training for 4 weeks.

Group 2

Forty participants are randomised into the control group and receive a health consultation that highlights the importance of physical activity and balance exercise according to standard practice within the HAI project. They are asked to return after 4 weeks for follow up.

Follow up

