Participants will also be asked to perform the Time-Up-and-Go (TUG) test,¹⁸ commonly used by clinicians to assess lower leg muscle strength, gait performance and overall functional mobility in elderly individuals. Testing involves participants rising unaided from an armchair and walking forward 3 meters until they reach a selected line on the floor, at which point they turn and come back to a seated position. Research nurses provides instructions and measures total testing time using a stopwatch. The TUG test have previously demonstrated good inter-

rater reliability (ICC=0.99).¹⁸ Testing of isometric muscle strength involves using a hydraulic hand dynamometer (Jamar, Patterson Medical, Warrenville, IL, USA) to measure participant's maximum grip strength in the non-dominant hand. Participants will be instructed to keep the arm angled at 90° and maintain the elbow in proximity to the waist during the test. The maximum value out of 2 consecutive attempts is subsequently recorded.

Measurement of Confidence in Balance Ability and Fear-of-Falling

Participants will also be asked to report confidence in balance ability and fear of falling. This will be accomplished through two questionnaires. The Falls Efficacy Scale International (FES-I) measures fear of falling and is comprised of 16 questions on a scale from 1-4.¹⁹ The Original Falls Efficacy Scale (FES) is also included and measures confidence in balance ability, formed by answering 13 questions on a scale from 1-10.²⁰

Anthropometric measures

Anthropometric data will be obtained using a scale (HL 120; Avery Berkel, Fairmont, MN, USA) to measure weight, and a gauge (Holtain Limited; Crymych, Dyfed, UK) to measure height.

Statistical analysis plan

Descriptive data will be presented as means + standard deviations and the Student's t-test will be used to analyze statistical differences between variables. Categorical variables are investigated using chi-squared tests. Potential differences between intervention and control group will be analyzed using paired and independent t-tests. All analyses will be performed with SPSS version 24 (IBM Corp, Armonk, NY, USA) and Stata version 13.1 (StataCorp, College Station, Texas, USA).

Ethical considerations

Importance

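### If the qualifying HAI sway value serves as the 'before' value, the planned paired t-tests can show a sway reduction with no training effect; the SAP should make the between-arm comparison primary

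*Combined protocol and SAP*

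**What the plan says.** Four parts of the combined protocol and SAP bear on this point.

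- **Selection.** The section on recruitment from the Healthy Ageing Initiative states: "Participants in HAI identified as being in the highest quartile of measures of postural sway, indicating poor balance and high fall risk, are invited". Those who agree "will upon agreement be randomized into either the intervention group or control group".
- **Aim.** The last paragraph of the background describes the aim as finding out "if we can reduce the increased postural sway of participants who have been identified as having abnormal balance values, based on previous measurements". Specific aim 1 asks whether four weeks of training improves sway, and does not add a comparison with control.
- **Measurement.** Both arms are measured again at 4 weeks with the HAI instruments. A baseline is named in the heading over the measurement methods. The visible text does not say whether it is the HAI test that qualified the person or a new test.
- **Analysis.** The statistical analysis plan says: "Potential differences between intervention and control group will be analyzed using paired and independent t-tests". It names no primary test, does not say what is paired with what, and includes no baseline adjustment.

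**The concern.** A group chosen because one noisy measurement was high will, on average, score lower at the next measurement even if nothing is done. Here the selection variable is the outcome variable. If the qualifying value is the 'before' value, the before-after change in the trained arm is the sum of regression to the mean, any repeat-test effect and any training effect. A paired t-test cannot separate the three.

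The two arms are not matched to each other, so the natural use of a paired t-test here is within an arm. Because aim 1 is worded without a comparator, a significant paired result in the trained arm could be offered as the answer to it. In the larger control arm the same artefact is more likely to reach significance, and could be taken for an effect of the consultation.

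**Working it through.** The plan gives no sample-size calculation, effect size or SD, so there is no figure to reproduce. The check asks how often a within-arm paired test would show a significant reduction if training did nothing.

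**Inputs from the documents**
- Selection: the highest quartile of sway.
- Arm sizes, from the intervention protocol: "Twenty participants are randomised into the intervention group" and "Forty participants are randomised into the control group". The recruitment section says "We aim to recruit 90 individuals from the existing HAI study cohort". Since 20 + 40 = 60, not 90, these statements need reconciling. I use 20 and 40, and add 45 per arm as an alternative (an even split of 90 is my assumption).

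**Assumptions**
- Sway is normal, in units of the population SD, and the same sway measure is used for selection and outcome.
- The correlation r between the qualifying test and the 4-week test is 0.6 to 0.95. The protocol reports agreement with other equipment but no test-retest correlation.
- Tests are two-sided at 5%, so the nominal rate for a significant reduction is 2.5%.
- There is no real change and no practice effect.

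**Step 1: mean and variance of those selected.** The cut is c = 0.674. The mean is m = φ(c)/0.25 = 0.3178/0.25 = 1.271. The variance is 1 + c·m − m² = 1 + 0.857 − 1.616 = 0.242 after rounding.

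**Step 2: expected drop with no training effect.** Drop = m(1 − r) = 1.271 × (1 − r). For r = 0.8 this is 1.271 × 0.2 = 0.25 SD.

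**Step 3: SD of the individual change.** SD = √[(1 − r)² × 0.242 + (1 − r²)]. For r = 0.8 this is √(0.0097 + 0.36) = 0.61.

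**Step 4: chance of a significant reduction.** This is the upper tail of a noncentral t with n − 1 degrees of freedom and noncentrality (drop/SD)·√n, beyond the usual two-sided critical value. For r = 0.8 and n = 20 the noncentrality is 0.418 × 4.47 = 1.87, the critical value is 2.093, and the chance is 43%. Simulation from the truncated distribution agrees within about one percentage point throughout.

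| r | Expected drop (SD) | n = 20 | n = 40 | n = 45 |
|---|---|---|---|---|
| 0.6 | 0.51 | 74% | 97% | 98% |
| 0.7 | 0.38 | 60% | 90% | 93% |
| 0.8 | 0.25 | 43% | 73% | 78% |
| 0.9 | 0.13 | 23% | 43% | 48% |
| 0.95 | 0.06 | 14% | 24% | 26% |

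**Step 5: the two alternatives, by simulation** (20,000 null trials per scenario, r from 0.5 to 0.95, arms 20:40 and 45:45).
- Paired test against a new baseline taken after selection: significant reduction in 2.4% to 2.7% of trials, which is the nominal rate.
- Independent t-test between arms, on change or on the 4-week value: type I error 4.5% to 5.4%, which is nominal even when the qualifying value is the baseline.

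**The case against.** The strongest reply is that the design already deals with the main threat. Both arms come from the same selected pool and are randomised after selection, so regression to the mean is equal in expectation in both. The SAP sentence that mentions paired tests is about differences between the arms and names the independent test too. This stands. A reader might infer that the trial's treatment effect is biased, or that a paired test is meant to decide aim 1. The documents support neither.

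A reader might also infer that a spurious reduction is bound to appear. That requires the qualifying value to be the 'before' value, and the text is open on this. The heading over the measurement methods refers to baseline as well as follow-up, the procedures are partly written in the future tense, and controls are asked to return after 4 weeks, which fits an in-person visit at trial start. On the other side, the aim refers to earlier measurements, and the sequence described is a telephone invitation and then randomisation, with no sway test mentioned in between. Figure 1, which was not available for this review, may show a baseline visit.

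Finally, the percentages depend on assumptions. At r = 0.95 the inflation is much smaller, though still several times nominal. The protocol does not say whether eyes-open or eyes-closed sway defined the quartile; for a condition not used for selection, the drop depends on other correlations. No limit is put on the age of the qualifying test, so real change in sway since then could add to the drop or offset it.

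What the reply leaves untouched is that paired tests are a stated method with no defined role. The control arm does not protect a p-value computed within one arm.

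**Conclusion.** The concern holds conditionally. If the qualifying HAI value is the 'before' value, a within-arm paired test can show a significant sway reduction from an ineffective programme in about 74% to 14% of trials with 20 participants and 97% to 24% with 40, for r from 0.6 to 0.95, against 2.5% nominal. The sizes rest on the assumed correlation, normality and no real change between tests. Under that model, any r below 1 gives a drop.

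If a new baseline is taken after selection, regression to the mean no longer affects the paired test. That test still cannot tell training from familiarity with the task, and still does not estimate a difference between arms. This is therefore a gap in the SAP about which analysis answers aim 1 and which measurement is the baseline. It is not a demonstrated bias in the randomised comparison.

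**What to change.** In the statistical analysis plan:

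1. Make the between-arm comparison of 4-week sway, adjusted for baseline sway by ANCOVA, the primary analysis for aim 1.
2. Report before-after changes for both arms side by side as descriptive only, with a note that participants were selected for high sway. State that these changes are not evidence of efficacy.
3. State which measurement is the baseline. Where a balance-board test is done at trial start in both arms, use it as baseline and keep the qualifying HAI value for eligibility only. If no such test is done, say so; the between-arm comparison remains unbiased with the HAI value as covariate.

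The cost is a few sentences of SAP text and slightly more analysis work. The downside is that the headline before-after improvement is likely to be smaller. If a fresh baseline was always intended, one sentence settles item 3, but items 1 and 2 are still needed.

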After 4 weeks, the groups are followed up with the same measures that are used in the Healthy Ageing Initiative that contains objective and functional balance tests, tests of muscle strength and a validated questionnaire on fear-of-falling and physical activity. Both groups will be offered the specific program for balance training post measurements, with instructions that it can be performed in the home setting according to the same principles offered to the intervention group. The groups are followed up after 6 and 12 months through 70-years-health checks on prospective falls and levels of physical activity.

Methods used for baseline and follow up

Measurements of postural stability

Postural stability is assessed using a Wii Balance Board (WBB) device (Nintendo, Kyoto, Japan) labeled “Nintendo RVL-WBC-01”, with a nominal sampling frequency of 100 Hz. The equipment is linked to a PC via Bluetooth connection “E1310E(00**”, using drivers labeled

intervention
three supervised
minutes of balance

“Manage Library for Nintendo’s Wiimote v1.7.00 by Brian Peek”. The software was designed in Microsoft C# by [name], Umeå University. The equipment’s power supply has been exchanged from battery to USB power. The validity and reliability of the WBB has been evaluated elsewhere, showing excellent conformation to other laboratory balance equipment, with mean differences in center of pressure (COP) variance ranging between 0.3 to 3%.¹³

Participants are examined during quiet stance involving trials of eyes open (EO) and eyes closed (EC) for 60 seconds each. Participants are instructed to maintain an upright position throughout the test and stand relaxed, while avoiding any arm or head movements. The WBB measures total COP sway length, representing the sum of postural sway in anteroposterior and

Measurements of physical activity and capacity

Participants will be asked to complete the short form of the International Physical Activity Questionnaire (IPAQ),¹⁷ an instrument designed to estimate activity levels among adult populations in domains including: 1) leisure time PA, 2) domestic and gardening activities, 3) work-related PA and 4) transport-related PA. Individuals are asked to recollect the duration of activities (walking, moderate- and vigorous- intensity PA) during the last 7 days in each domain. Questionnaire responses are used to calculate MET-min data in accordance with IPAQ guidelines.¹⁷

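### Randomisation is triggered by agreement after a telephone invitation, no trial baseline is required before allocation, and the baseline itself is undefined

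*Combined protocol and SAP*

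**What the plan says.** All references are to the combined protocol and SAP.

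- **Study population, recruitment from HAI.** The eligible group is "Participants in HAI identified as being in the highest quartile of measures of postural sway". They "are invited to participate by telephone contact, and will upon agreement be randomized into either the intervention group or control group". The next paragraph adds: "Participants will after the initial contact also receive written information about the study".
- **Background, closing aim.** The trial concerns "participants who have been identified as having abnormal balance values, based on previous measurements", so a sway reading exists for every invited person before allocation.
- **Methods.** A baseline is named only in the heading "Methods used for baseline and follow up". It has no date and no stated position relative to randomisation.
- **Follow up.** After 4 weeks "the groups are followed up with the same measures that are used in the Healthy Ageing Initiative". This would allow the HAI visit to serve as the baseline, but the text does not say that it does.
- **Confidence in balance and fear of falling.** "Participants will also be asked to report confidence in balance ability and fear of falling". These are the FES-I and FES, both self-reported. The TUG is timed by a research nurse with a stopwatch.
- **Statistical analysis plan.** Paired and independent t-tests are planned. There is no analysis set, no rule for people who leave after randomisation, and no adjustment for baseline.
- **Study protocol.** The reader is sent to figure 1, which is not shown in the text reviewed and may give the sequence.

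**The concern.** The only stated trigger for randomisation is agreement following a telephone invitation. Followed literally, a person can be allocated, learn the arm and withdraw before the trial has measured anything. Only the training arm has to attend supervised group sessions, so uneven withdrawal at that moment is plausible. With 20 people in that arm, each one who leaves is 5% of it (1/20).

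The undefined baseline adds a second problem, which depends on what the baseline turns out to be:

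- **Measured after allocation.** Those who stay complete the FES-I, FES and TUG knowing their arm. The two questionnaires carry the aims on confidence and fear of falling, so the starting values for those aims could shift with the allocation.
- **Taken from HAI.** Allocation cannot affect the reading. However, it is of unstated age (HAI began in 2012), and for sway it is the very value that marked the person as extreme. A later reading would be expected to be lower without any training.

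**Working it through.** The documents give no SD, correlation, dropout rate, alpha or power, so there is no planned figure to reproduce. The arm sizes of 20 and 40 come from the Intervention protocol section. Everything else below is assumed, and a two-sided 5% test is used.

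**1. Order of events.** The recruitment text gives invitation, agreement, randomisation. Written information is fixed only as following the first contact. Baseline testing has no place in the sequence. Controls are asked to come back at 4 weeks, which suggests an initial visit, but nothing says that it precedes allocation.

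**2. Loss between allocation and baseline (illustration).** Assume no true effect, a share d of the trained arm leaving, none of the control arm leaving, and leavers swaying g SD more than stayers. The remaining trained arm then has mean sway lower by

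bias = d × g.

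- d = 0.10, g = 0.5: 0.05 SD
- d = 0.20, g = 0.5 to 1.0: 0.10 to 0.20 SD
- d = 0.30, g = 1.0: 0.30 SD

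The standard error is √(1/(20(1−d)) + 1/40).

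- d = 0.10: √(1/18 + 1/40) = 0.284
- d = 0.30: √(1/14 + 1/40) = 0.311

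With k = bias/SE, the type I error is Φ(−1.96 + k) + Φ(−1.96 − k).

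- Low end: k = 0.05/0.284 = 0.18, giving 5.4%
- High end: k = 0.30/0.311 = 0.97, giving 16.2%

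Simulation of 40,000 trials, with leavers chosen by a latent variable correlated with sway, gives:

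| Loss in trained arm | Type I error, g = 0.5 | Type I error, g = 1.0 |
|---|---|---|
| 10% | 5.2% | 6.2% |
| 20% | 6.0% | 9.6% |
| 30% | 7.2% | 14.8% |

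The range is therefore about 5% to 15%. If g = 0, bias is 0 and type I error stays at 5%. If g is negative (steadier people leave), the bias works against training.

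**3. HAI reading as baseline.** For a normal variable, the mean of the top quartile is φ(0.674)/0.25 = 1.27 SD above the population mean. With correlation r between the HAI and week-4 readings, the expected fall without any effect is (1 − r) × 1.27, in HAI population SDs.

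- r = 0.8: 0.25 SD
- r = 0.5: 0.64 SD

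Simulated with no true effect, a paired t-test shows a significant reduction in sway at these rates:

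| Arm size | r = 0.8 | r = 0.5 |
|---|---|---|
| 20 | about 42% | about 85% |
| 40 | about 73% | about 99% |

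The expected fall is the same in both arms, so it cancels in the between-arm comparison.

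**The case against.** The strongest reply is that the order is partly inferred. Agreement as the trigger can be read as a condition rather than a moment during the call, and figure 1 may show a sound sequence. That stands as a caution. But if the figure does show one, the recruitment sentence still needs to match it.

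A reader might infer four stronger points that the documents do not support:

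- **That people are randomised before they receive written information.** This is a natural reading, but the text places the information only after the first contact and does not relate it to randomisation.
- **That leavers have no earlier data and their loss cannot be corrected.** Every invited person has an HAI sway reading, because it defines eligibility. Partial adjustment is possible. The gap is that the SAP plans none.
- **That arm-dependent baseline scores and regression to the mean both apply.** For any one measure they belong to alternative readings: the first needs a baseline taken after allocation, the second needs the HAI reading. The text does not settle which holds.
- **That the order alone produces a bias of 0.05 to 0.30 SD.** Those figures assume one-sided loss of poorer balancers. Controls must also return at 4 weeks, and fitter people might decline training. People can also leave after a proper baseline, with the same effect on an unadjusted week-4 t-test.

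It can also be said that the cost exceeds a change of wording if no baseline session is planned. That is correct.

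**Conclusion.** The concern holds in this limited form. The text ties randomisation to agreement after a telephone invitation, requires no trial baseline before allocation, and does not say whether the HAI visit is the baseline. This permits loss that depends on the arm before any trial measurement, and the SAP does not address such loss.

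The regression-to-the-mean result applies only if the HAI reading is the baseline, and then only to the within-arm paired tests. It rests on normality and on assumed correlations. The loss figures are an illustration at 20:40. The recruitment target of 90 does not match 20 + 40 = 60 and must be reconciled; larger arms would raise the type I error for the same bias.

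The sponsor should change this before recruitment, because the order cannot be restored once people are randomised. Confidence is medium, since figure 1 is not shown.

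**What to change.** Reword the recruitment paragraph along these lines:

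*People who agree by telephone receive the written information, give consent and complete the baseline tests (WBB, TUG, grip strength, FES-I, FES, IPAQ). Only then are they randomised from a concealed list and told their arm. The earlier HAI reading determines eligibility only; the new reading is the baseline in all analyses.*

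Make the text and figure 1 agree.

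This prevents loss between agreement and baseline, but not loss after it. The SAP should therefore also:

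- analyse all randomised people in their allocated arm;
- make the main comparison between arms, adjusted for baseline (ANCOVA);
- report losses by arm and by timing.

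**Cost.** The wording changes are short. Some extra calls will be needed to replace people who agree but do not attend baseline. If no baseline session is currently planned, one must be added for each person.

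### The recruitment target of 90 does not match the stated arm sizes, 20 + 40 = 60, and the readable text does not say which total governs

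*Combined protocol and SAP*

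**What the plan says.** Four statements in the combined protocol and SAP bear on the size of the trial.

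- **Study population**, target: "We aim to recruit 90 individuals from the existing HAI study cohort".
- **Study population**, route into the trial: Healthy Ageing Initiative participants with high postural sway are invited by telephone and "will upon agreement be randomized into either the intervention group or control group". Written information follows the first contact.
- **Intervention protocol, Group 1**: "Twenty participants are randomised into the intervention group".
- **Intervention protocol, Group 2**: "Forty participants are randomised into the control group and receive a health consultation".

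The Statistical analysis plan adds only the method: "Potential differences between intervention and control group will be analyzed using paired and independent t-tests". It contains no sample size calculation, significance level, power, effect size, standard deviation, allocation ratio or dropout rate. The Study protocol section points to a figure 1, which was not available to this review.

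**The concern.** The target and the two arm sizes are the only statements of trial size in the readable text, and they disagree. With no sample size calculation to fall back on, a reader cannot tell whether 60 or 90 people are planned, how many go to each arm, or whether the 1:2 ratio implied by 20 and 40 is intended.

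Two things are at stake. The first is the plan's value as a record made in advance: stopping at 60 and continuing to 90 could each be presented later as following it. The second is the precision of the between-group t-test, which depends on the arm sizes. The mismatch does not in itself bias that comparison.

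**Working it through.** **Inputs.** Target 90 (Study population); intervention arm 20 (Group 1); control arm 40 (Group 2).

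**Step 1: try to reproduce the target.**

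- Sum of the arms: 20 + 40 = 60, not 90.
- Shortfall: 90 − 60 = 30.
- As a share of the target: 30/90 = 33.3%.

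**Step 2: look for something that accounts for the 30.**

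- *A third arm.* Only Group 1 and Group 2 are described.
- *Loss between agreement and randomisation.* The Study population text randomises people when they agree. It gives no run-in, later eligibility step or expected loss.
- *A dropout allowance, N/(1 − d).* Setting 60/(1 − d) = 90 gives d = 1 − 60/90 = 33.3%. For comparison, 10% gives 60/0.9 = 67 (rounded up) and 20% gives 60/0.8 = 75.
- *A dropout allowance in the cruder form, N × (1 + d).* Setting 60 × (1 + d) = 90 gives d = 50%. The plan states no dropout rate of any size. It also describes 20 and 40 as numbers randomised, not numbers completing.
- *Damage to the text in conversion from PDF.* Part of the Group 1 training sentence is displaced into the section on measuring postural stability. The displaced words concern the training sessions and none is a participant number. The target and both arm-size statements read cleanly.

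**Step 3: illustrate what the ambiguity means for precision.** The plan gives none of the quantities needed, so these are assumptions: two-sided 5% level, 80% power, equal SDs in the arms, independent t-test with power from the noncentral t distribution. The standard error of the difference in SD units is √(1/n₁ + 1/n₂), and the 95% confidence interval half-width is t(0.975, n₁ + n₂ − 2) times that.

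Only 20:40 comes from the plan. The other rows are ways in which 90 could be split: keep the intervention arm at 20, keep the implied 1:2 ratio, keep the control arm at 40, or allocate equally.

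| Intervention:control | Total | SE (SD units) | Detectable difference, 80% power | Power at 0.6 SD | 95% CI half-width |
|---|---|---|---|---|---|
| 20:40 | 60 | 0.274 | 0.78 SD | 58% | 0.55 SD |
| 20:70 | 90 | 0.254 | 0.72 SD | 65% | 0.50 SD |
| 30:60 | 90 | 0.224 | 0.63 SD | 76% | 0.44 SD |
| 50:40 | 90 | 0.212 | 0.60 SD | 80% | 0.42 SD |
| 45:45 | 90 | 0.211 | 0.60 SD | 80% | 0.42 SD |

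Example for 20:40: √(1/20 + 1/40) = √0.075 = 0.274. The normal approximation (1.960 + 0.842) × 0.274 gives 0.77 SD; the noncentral t raises this to 0.78 SD.

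**The case against.** The strongest reply is that recruiting and randomising are different acts. Figure 1 is a study diagram, and it could show 90 recruited and 60 randomised. The text would then be incomplete rather than contradictory. The order of telephone agreement, written information and randomisation is not fully set out, so some withdrawal before randomisation is conceivable.

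Part of this stands. Without figure 1, one can say only that the readable text does not settle which total governs, and reading 90 as the number approached or screened cannot be excluded. The fix allows for it. But the text does not support that reading: it randomises people on agreement and gives no count or rate of loss. If the figure does show such a step, the text still has to say so.

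It can also be said that the precision figures rest on assumptions and on splits the plan never mentions, and that no stated power claim fails because none is made. That is correct. The figures show only that the choice of total matters; the documented discrepancy is 30 of 90.

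Finally, a discrepancy that causes no bias and is cured by rewording might be thought minor. Against that, planned enrolment and allocation are basic design facts, and nothing else in the readable text fixes them.

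**Conclusion.** The concern holds. As written, the plan gives two incompatible totals, 90 recruited and 60 randomised. One third of the target has no stated arm, and the readable text offers no explanation. This conclusion needs only the three stated numbers and the absence of any reconciling statement in the text available; figure 1 was not seen.

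Under the assumptions in the working, the difference detectable with 80% power ranges from 0.78 SD at 20:40 to 0.60 SD at 45:45, depending on which total and split is meant. This should be corrected before the plan is relied on, although it does not bias the comparison. Which number was intended cannot be determined from the document.

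**What to change.** State one total and two arm sizes that add up to it, with the allocation ratio. Use the same numbers in the Study population, Group 1 and Group 2 text, and in figure 1 if it carries counts.

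- If 20:40 is the design, change the target to 60.
- If 90 is the design, change the arm sizes so that they sum to 90.
- If 90 is the number approached or screened, say so and state how many are randomised.

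The cost is wording only, provided the text is aligned to the number actually planned. If 60 is the real plan, moving to 90 would mean 30 more participants; that is a resource decision and not part of this correction. A sentence giving the detectable difference for the chosen numbers, with its significance level and power, would be useful but is not needed to resolve the mismatch.
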